#### **10.4. Treatment Compliance**

A listing of planned and actual treatments will be produced.

A listing of drug accountability data (date, actual dose, total volume infused) will be produced.

A summary of overall compliance for study drug based on the exposure data will be produced. Compliance will be based on the total dose of ofatumumab received (mg) divided by the total dose (mg) expected taking into account withdrawal from treatment. Therefore, the denominator is based on the total dose received during the time that a subject is actually eligible to receive drug. The calculation of overall compliance is based on the entire interval of dosing for [specify treatment(s)]. The formula for daily dose medication is compliance (%) = [total cumulative actual dose / (duration of study treatment \* prescribed dose)]\*100 where duration of study treatment is last dose-first dose +1.

For example, if the dosing period for a study is one year and during that year, a subject received 100 mg of drug each month, then the denominator (total dose expected) would be 1200mg as a total dose if the subject was actually in the study for the full year. However, if the subject discontinued treatment at the end of the 6th month, then total dose in mg expected for this case would be 600 mg.

Percentage overall compliance will be summarized using the mean, standard deviation, minimum, median, and maximum. In additional, percentage overall compliance will be categorized and summarized by <80%, 80%-105%, and >105%.

In addition, summaries of study treatment exposure and dose modifications (e.g., number of dose reductions, number of dose interruptions) will further characterize compliance. These analyses are described in Section 12.1 ‘Extent of Exposure’.

## 10.5. Concomitant Medications

Concomitant medications will be coded using GSK Drug coding dictionary, summarized, and listed. The summary of concomitant medications will show the number and percentage of subjects taking concomitant medications by Ingredient. Multi-ingredient products will be summarized by their separate ingredients rather than as a combination of ingredients. Anatomical Therapeutic Chemical (ATC) classification Level 1 (Body System) information will be included in the dataset created but will not appear on the listing or summary.

In the summary of concomitant medications, each subject is counted once within each unique ingredient. For example, if a subject takes Amoxicillin on two separate occasions, the subject is counted only once under the ingredient “Amoxicillin”.

Blood products or blood supportive care products with onset date within the on-therapy window will be included in the summary tables. The frequency and percentage of subjects using blood products and blood supportive care products after the start of study medication will be provided. Supporting listings will also be provided.

Concomitant medications will be summarized separately for medications with onset date within the on-therapy period and for medications with onset date within the pre-therapy period. Note: In order to be considered a concomitant medication, the concomitant medication must have been taken at some point during the on-therapy window.

## 10.6. Subsequent Anti-Cancer Therapies

The number and percentage of subjects that received chemotherapy, immunotherapy, hormonal therapy, biologic therapy, radioactive therapy, and small molecule targeted therapy as post study treatment anti-cancer therapy will be summarized. Time from study treatment discontinuation to the first post study treatment anti-cancer therapy will also be included in this summary table.

Follow-up anti-cancer therapy will be coded using GSK Drug coding dictionary, then summarized by ingredient. A listing of the type of follow-up anti-cancer therapy received (chemotherapy, immunotherapy, hormonal therapy, biologic therapy, radioactive therapy, small molecule targeted therapy) for each subject will be provided.

## 11. EFFICACY

All efficacy analyses will be based on the ITT population as defined in Section 6 unless otherwise specified. All analyses will be presented by treatment arm.

Efficacy assessments are based on IWCLL updated NCI-WG CLL criteria (Hallek, 2008) to assess clinical activity and disease status. Primary assessments will be based on

investigator assessment. Independent Reviewer Committee assessments will be considered as supplementary for sensitivity analyses.

## 11.1. Primary Efficacy Analysis

### Progression-Free Survival

The primary endpoint, progression-free survival (PFS), is defined as the interval of time (in months) between the date of randomization and the earlier of the date of disease progression or death due to any cause. The investigator assessment of response will be used for the primary analysis. Details on censoring are provided in [Table 1](#).

**Note that events of disease progression determined by CT scan will be excluded from the primary analysis of PFS but will be included in a sensitivity analysis.**

The date of documented disease progression will be defined as the date of disease progression based on investigator assessment. The date of death should be taken from the Record of Death page. Death on study due to any cause will be included as an event for calculation of PFS.

If there is no adequate baseline assessment, the subjects will be censored at their date of randomization. Subjects without any adequate post-baseline assessments will be censored at the date of randomization.

Subjects who progressed or died after an extended period without an adequate assessment will be censored at their date of last assessment prior to progression or death even if subsequent information is available regarding progression or death. An adequate assessment is defined as an assessment where the investigator determined response and components of lab and clinical parameters (blood, lymph nodes, organ and constitutional symptoms) are available. The blood laboratory tests in the definition of the “adequate assessment” are haemoglobin, platelets, ANC and lymphocytes. The date of response at that assessment will be used for censoring. As the assessment schedule may change through the course of the protocol, specific rules for identifying extended loss to follow-up or extended time without an adequate assessment are provided in [Section 9](#).

For subjects who receive subsequent anti-cancer therapy, the following rules will apply:

- If the start date of the anti-cancer therapy is partial (i.e. either missing the day but has the month and year available or missing both day and month) the imputation rules described in [Section 9](#) will be applied. No imputation will be made for completely missing dates.
- If anti-cancer therapy is started without documented disease progression or is started prior to documented disease progression, then PFS will be censored at the date of the last adequate assessment that is no later than the date of initiation of anti-cancer therapy (i.e. if an assessment occurs on the same day as the start of new anti-cancer therapy the assessment will be used as it will be assumed the assessment occurred prior to the administration of new anti-cancer therapy). The date of response at the last adequate assessment will be used as the censoring value.

- If a subject has only a baseline visit or does not have an adequate assessment that is not later than the date of initiation of anti-cancer therapy, PFS will be censored at the date of randomization.

If a subject has not progressed, has not died or has not started new-anti-cancer therapy, then PFS will be censored at the date of the last adequate assessment defined as an assessment where the investigator determined response and components of lab and clinical parameters (blood, lymph nodes, organ and constitutional symptoms) are available. The date of response will be used as the censoring date.

The assignments for progression and censoring dates for PFS are specified in the following table

**Table 1 Assignments for Progression and Censoring Dates for PFS Analysis**

Situation	Date of Event (Progression/Death) or Censoring	Outcome Event (Progression/Death) or Censored
No (or inadequate) baseline response assessment and the subject has not died	Randomization	Censored
No post-baseline response assessments and the subject has not died	Randomization	Censored
Progression documented between scheduled visits	Date of assessment of progression	Event
No progression (or death)	Date of last adequate assessment of response 	Censored
New anticancer treatment started (prior to documented disease progression) 	Date of last adequate assessment of response  (on or prior to starting anti-cancer therapy)	Censored
Death before first PD assessment (or Death at baseline or prior to any adequate assessments)	Date of death	Event
Death between adequate assessment visits	Date of death	Event
Death or progression after more than 2.5 missed visits	Date of last adequate assessment of response (prior to missed assessments)	Censored

An adequate assessment is defined as an assessment where the investigator determined response and components of lab and clinical parameters (blood, lymph nodes, organ and constitutional symptoms) are available. The blood laboratory tests in the definition of the “adequate assessment” are haemoglobin, platelets, ANC and lymphocytes.

If PD and new anti-cancer therapy occur on the same day, assume that progression was documented first (i.e. outcome is progression and the date is the date of the assessment of progression). If anti-cancer therapy is started prior to any adequate assessments, censoring date should be the date of randomization.

An interim analysis of the primary endpoint, PFS, will be performed when 2/3 of the total number of events have occurred (187 events). The interim analysis for PFS will be performed by an IDMC utilizing a significance level of 0.001. The interim analysis of PFS will be conducted in the same manner as described for the final analysis. Details of the interim analysis are also provided in the IDMC Charter.

The final analysis of PFS will be based on a two-sided test with a significance level of 0.0498. The survival distributions will be estimated using Kaplan-Meier survival curves and will be compared using a stratified log-rank test. The Pike estimator [Berry, 1991] of the treatment hazard ratios (HR) will be provided, together with the 95% Confidence Interval (CI). The Pike estimator, which is a nonparametric estimator of the HR, has been specifically developed for survival data and is used as a measure of the relative survival experience of two groups. Within the range of values of the ratio of the hazard rates of interest in clinical trials, the Pike estimator is more efficient in terms of mean square error than the Cox proportional hazard method [Bernstein, 1981]

If there are a sufficient number of progressions or deaths, median PFS, first and third quartiles and 95% CI, will be estimated using the Brookmeyer-Crowley method [Brookmeyer, 1982]. A figure and listing of progression-free survival time will also be provided.

A supplementary table showing the details of the number at risk, number of events, and number censored with the event time will also be produced. Estimates of median PFS after 6 months, 1 year and 2 years of exposure (or observation) will also be provided.

In addition to the stratified log-rank test based on the Kaplan-Meier procedure, a Cox regression model using a stepwise procedure will be used and will include covariates for treatment, stratification factors [CR or PR at study entry; number of previous induction treatments; and type of prior treatment (chemoimmunotherapy, only alkylating monotherapy, or other treatment)] and other baseline data deemed appropriate such as age, Binet stage and baseline cytogenetics data. Treatment will remain forced in the model. An entry/removal significance level of 0.05 will be used. Analytical results will include the estimated hazard ratios along with 95% confidence intervals and associated probabilities for the effect of treatment, stratification factors, and the covariates. The hazard ratio for treatment will express the risk of experiencing disease progression or death for ‘ofatumumab maintenance’ vs ‘observation’ (i.e., no further treatment).

PFS will be evaluated for the ITT population. If the ITT population and Per Protocol population differ by more than 10%, then PFS will also be evaluated for the Per-Protocol population to check the robustness of the result when using the ITT population.

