8.3.5.1. Efficacy Analyses

Primary Analysis

The primary endpoint is progression-free-survival which is defined as the time from randomization to the date of disease progression or death due to any cause. The investigator assessment of response will be assessed according to the IWCLL updated NCI-WG CLL criteria [Hallek, 2008].

An interim analysis of the primary endpoint, PFS, will be performed when 2/3 of the total number of events have occurred (187 events). The interim analysis for PFS will be performed by an IDMC utilizing a significance level of 0.001. The interim analysis of PFS will be conducted in the same manner as described for the final analysis, and further details of the interim analysis will be provided in the IDMC Charter.

The final analysis of PFS will be tested based on a two-sided test with a significance level of 0.0498. The survival distributions will be estimated using Kaplan-Meier survival curves and will be compared using a stratified log-rank test.

In addition to the stratified log-rank test based on the Kaplan-Meier procedure, a Cox regression model will be used and will include covariates for treatment, stratification factors, and other baseline data deemed appropriate. Analytical results will include the estimated hazard ratios along with 95% confidence intervals, and associated probabilities for the effect of treatment, stratification factors and the covariates. The hazard ratio for treatment will express the risk of experiencing disease progression or death for ‘ofatumumab’ vs ‘no further treatment’.

Table 7 PFS Assignment

Situation	Date of Progression or Censoring	Outcome
No baseline tumour	Randomization	Censored
Progression documented between scheduled visits	- Date of assessment of new lymph node (if progression is based on new lymph node) - Date of last assessment (if progression is based on increase in sum of measured lymph nodes)	Progressed
No progression (at end of trial)	Date of last assessment of measured lymph nodes	Censored
Treatment discontinuation for undocumented progression	Date of last assessment of measured lymph nodes	Censored
New anticancer treatment started	Date of last assessment of measured lymph nodes	Censored
Death before first assessment	Date of death	Progressed
Death between adequate assessment visits	Date of death	Progressed
Death or progression after more than one missed visit	Date of last assessment of measured lymph nodes	Censored

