## 8.2. Other Strata and Covariates

In all efficacy analyses, the tests will be stratified by the baseline stratification factors: (1) CR or PR at study entry, (2) number of previous induction treatments (2 vs 3) and (3) type of prior treatment : chemoimmunotherapy, only alkylating monotherapy, or other treatment. The demographic summaries will document the number of subjects who fall into each stratum for the ITT population. PFS, the primary endpoint, will also be summarized according to the stratification factors.

Subjects will be considered to fall into the respective stratification categories according to the actual data given in the eCRF. Hence, if any misallocations took place in the stratification, it will be the actual data which will be used to determine the stratification of the subject rather than the data as recorded on RAMOS.

In addition to stratification factors, treatment arm as well as age, gender and race will be considered as covariates in the Cox regression model to assess the effect of ofatumumab maintenance treatment vs. no further treatment.

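### The stepwise rule for the supportive PFS Cox model can drop the three randomisation factors that the protocol says the model will include

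*SAP*

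**What the plan says.** Protocol 8.3.5.1 adds a Cox model to the primary log-rank comparison: "a Cox regression model will be used and will include covariates for treatment, stratification factors, and other baseline data deemed appropriate". It mentions no variable selection.

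SAP 11.1 keeps the promise to include the factors but adds a selection procedure: "a Cox regression model using a stepwise procedure will be used and will include covariates for treatment, stratification factors", followed by other baseline data such as age, Binet stage and baseline cytogenetics. Two rules follow: "Treatment will remain forced in the model" and "An entry/removal significance level of 0.05 will be used". The planned output covers hazard ratios with "95% confidence intervals and associated probabilities for the effect of treatment, stratification factors, and the covariates".

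The wider candidate list differs between sections. SAP 8.2 says that, besides the stratification factors and treatment, "age, gender and race will be considered as covariates in the Cox regression model". SAP 9.2.14 gives a longer optional list that adds Rai and Binet stage, ECOG, MRD, cytogenetics at baseline and at relapse, and Ctau and Cmax at three occasions.

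The primary test is separate: "The survival distributions will be estimated using Kaplan-Meier survival curves and will be compared using a stratified log-rank test", with the Pike estimator for the hazard ratio.

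**The concern.** The SAP names treatment as the one protected term. Response at entry, number of previous induction treatments and type of prior treatment must therefore each pass p<0.05 to enter and to stay. That conflicts with the protocol, and with the SAP's own output, since a factor that has been removed has no hazard ratio, interval or p-value to report.

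Two things are at stake. The first is agreement between the supportive model and a design stratified on these factors. The second is the honesty of the factor and covariate estimates: those that survive a significance filter are exaggerated on average, and their nominal intervals take no account of the filter. No adjustment for selection is described, and SAP 11.1 plans no unselected Cox model as a check.

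**Working it through.** **1. Reproduce the plan's event count.** Inputs from protocol 8.2.1 and SAP 5.1: medians 28 and 39.2 months, two-sided 5%, 80% power, 1:1 allocation. Hazard ratio = 28/39.2 = 0.714, with |ln HR| = 0.3365.

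Events = 4 × (1.960 + 0.842)² / 0.3365² = 278 (Schoenfeld). Freedman's formula gives 283. The plan's 280 lies between them. With 280 events, √(280/4) × 0.3365 − 1.960 = 0.855, which is power 0.80, as stated. The same formula can therefore be used for the factors.

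**2. Chance that a real factor fails the 0.05 criterion.** For a binary factor with prevalence p and hazard ratio θ, with d events:

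P(fail) = 1 − Φ( √(d·p·(1−p)) × |ln θ| − 1.960 )

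Example with d = 280, θ = 1.3 and p = 0.5: √70 × 0.2624 − 1.960 = 0.235, so P(fail) = 1 − 0.593 = 41%. With p = 0.2: √44.8 × 0.2624 − 1.960 = −0.204, so P(fail) = 58%.

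| Factor HR | 280 events, p = 0.5 | 280 events, p = 0.2 | 187 events, p = 0.5 | 187 events, p = 0.2 |
|---|---|---|---|---|
| 1.2 | 67% | 77% | 76% | 83% |
| 1.3 | 41% | 58% | 57% | 70% |
| 1.5 | 8% | 23% | 21% | 40% |

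A factor with no effect is left out about 95% of the time. The hazard ratios and prevalences are assumptions, because the documents give none.

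**3. What selection does to the estimates.** The simulation used 478 subjects, accrual of 12 per month, and 187 or 280 events. The true treatment hazard ratio was 0.714 or 0.50. There were eight candidates: the three randomisation factors, age, Binet stage, cytogenetics, sex and race. Entry was by score test and removal by Wald test, both at 0.05, with treatment forced. The comparator kept all eight covariates. Mild effects set the randomisation factors at about 1.2 (or its inverse); moderate effects set them at 1.3 to 1.5. There were 600 trials per setting and seven settings in all (moderate effects with 187 events were run only for treatment hazard ratio 0.714).

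| Quantity | Stepwise | All covariates kept |
|---|---|---|
| 95% CI coverage, covariates, mild | 81% (187 events), 85% (280 events), selected only | 94.5–94.8% |
| 95% CI coverage, covariates, moderate | 92–93%, selected only | 94.3–95.1% |
| 95% CI coverage, treatment | 93.3–95.5% | 93.5–95.3% |

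At 280 events all three randomisation factors stayed together in about 2% of trials with mild effects and 23–27% with moderate effects. Selected covariates with a true effect had |log HR| inflated about 1.7-fold (mild) or 1.2-fold (moderate). The mean treatment hazard ratio differed between the two approaches by at most about 0.005. Monte Carlo error on a 95% coverage figure is √(0.95 × 0.05/600) = 0.9 percentage points, so the treatment coverages are indistinguishable.

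**4. Candidates that do not fit this model.** Protocol 6.6 collects pharmacokinetic samples only from subjects receiving ofatumumab, so Ctau and Cmax do not exist in the observation arm. Cytogenetics at relapse is measured after randomisation. Neither is baseline data in the sense of protocol 8.3.5.1.

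**The case against.** The strongest reply is that no inference depends on this model. The primary test is the stratified log-rank, gatekeeping runs through it, and the Cox fit is additional. That stands, and it limits the point to a minor one.

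A second reply is that SAP 11.1 still says the stratification factors are included, so the text is ambiguous rather than wrong. That stands in part. But naming treatment alone as forced would be unnecessary if the factors were already protected, so the rule as written does not protect them.

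Third, the open reference to other baseline data is the protocol's own, so an unfixed covariate list is not in itself a SAP departure. The method, the forced term and the selection level are all stated, so it would be too strong to call the model unspecified.

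Three stronger readings are tempting and are not supported:
- **Selection distorts the treatment hazard ratio.** Treatment is randomised and forced in, and step 3 shows almost no change in its estimate or coverage.
- **The chance that a pure-noise covariate enters measures the harm.** For independent null candidates it is 1 − 0.95³ = 14% for the three named in SAP 11.1 and 1 − 0.95¹⁵ = 54% for the fifteen listed in SAP 9.2.14. Several of these candidates are related or expected to be prognostic, and a null covariate barely moves a forced treatment effect.
- **The analysed sample changes from step to step.** Protocol 6.2.3 specifies baseline MRD for subjects entering in CR, and protocol 6.3.3 collects baseline cytogenetics only where possible. The SAP does not say how missing covariates are handled, and a complete-case fit would keep the sample fixed.

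Finally, timing. The SAP for the 280-event analysis retains the Cox output (Table 2.0020) and treats results as descriptive. The SAP for the final analysis says PFS will not be updated. A new model now would be post hoc, so it belongs beside the existing table with the reason stated.

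**Conclusion.** The point holds as a narrow one. As written, SAP 11.1 allows the three randomisation factors to be removed from the supportive PFS Cox model, contrary to protocol 8.3.5.1 and to the SAP's own promised output. Removal is likely enough to matter: 41–58% for a factor with hazard ratio 1.3 at 280 events, depending on prevalence. The intervals of covariates that survive selection are too narrow for what they claim, mainly when true effects are mild. The exact figures depend on assumed effect sizes and prevalences; the direction does not. A reader should not infer that the primary PFS result, its significance levels or the treatment hazard ratio is in doubt.

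**What to change.** In SAP 11.1, force treatment and the three stratification factors into the Cox model, or stratify the model by those factors. Align SAP 8.2 and 9.2.14 with it, and restrict further candidates to baseline covariates available in both arms, which removes Ctau, Cmax and cytogenetics at relapse from this model. Label any stepwise-selected prognostic model, with its covariate intervals and p-values, as exploratory. Where the stepwise table has already been produced, report the forced-factor model beside it and disclose the departure from the protocol in the study report.

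The cost is SAP wording and one simple model fit, with no new data and no effect on events or alpha. Restoring the protocol's model does not require banning all selection or choosing a particular further set such as age plus Binet stage; that would be a preference.
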